##### 11.1.3.1.2 PERIOD 2 (+24 weeks [optionally up to a maximum 12 months of P2Y12 inhibitor treatment after ACS underwent PCI, based on investigator's discretion])

Period 2 will include just safety analyses.

#### 11.1.3.2 Secondary Efficacy Analyses

##### 11.1.3.2.1 PERIOD 1 (4 weeks)

Percentage of High on-Treatment Platelet Reactivity (HTPR) defined as PRU > 235 will be summarized with their corresponding 95% confidence interval.

Percentage of platelet inhibition at the end of the 4-week MD treatment period, after switching from clopidogrel MD to prasugrel MD will be obtained together with its 95% confidence interval.

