##### **6.1.1.2 Secondary Objective(s)**

To assess the antiplatelet effect and safety of prasugrel from baseline to the end of the 4-week MD treatment period, after switching from clopidogrel MD to prasugrel MD. The antiplatelet effect assessments will include percentage of High on-Treatment Platelet Reactivity (HTPR) and percentage of platelet inhibition. The safety assessments will include major, minor and clinically relevant bleeding events, major adverse cardiovascular events (MACE), all cause deaths and adverse events.

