#### 8.4.1.7 Procedure for Clinical Laboratory Samples

Blood sampling for local assessment will be obtained at screening (visit 1), Day 1 (visit 2), week 4 (visit 3), week 16 (visit 4), week 28 (visit 5), optionally based on investigator's discretion at maximum 12 months of P2Y12 inhibitor treatment after ACS underwent PCI (visit 6) or early termination. All samples will be collected in accordance with acceptable laboratory procedures. Details of these procedures and required safety monitoring will be provided by the site and archived in the trial master file (TMF). There is no need for fasting conditions for the analyses; but the same fasting or fed conditions should remain the same for all the blood samples obtained and analyzed at the same site for all their corresponding patients. Blood samples obtained from day 1 to week 28 and optionally up to a maximum 12 months of P2Y12 inhibitor treatment after ACS underwent PCI will be taken before prasugrel MD + aspirin administration of each corresponding visit.

All laboratory values outside the normal range must be evaluated and assessed by the investigator for clinical relevance and in this case, they should be recorded in the eCRF as adverse events.

The clinical analyses will be performed in a local laboratory (including hematology, biochemistry and pregnancy testing). An extra blood sample will be obtained at visit 3 (week 4) once during the whole study for the pharmacogenomic central laboratory examination for patients who sign the pharmacogenomic informed consent form separately.

The following parameters will be assessed:

- Platelet function: P2Y12 reaction unit (PRU, also to derive the platelet reactivity [HTPR]), platelet inhibition (%). (See [Section 8.4.1.9](#))
- Hematology: White Blood Cells (WBC), neutrophils, lymphocytes, monocytes, eosinophils, basophils, Red Blood Cells (RBC), Hemoglobin, Hematocrit, Platelet Count.

- Biochemistry: Total protein, albumin, alanine aminotransferase (ALT), aspartate aminotransferase (AST), alkaline phosphatase, total bilirubin, blood urea nitrogen (BUN), creatinine, sodium, potassium, chloride, LDL cholesterol. The estimated glomerular filtration rate (eGFR) will be calculated following the CKD-EPI Creatinine Equation (2009).

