#### **8.4.1.9 Platelet function**

P2Y12 reaction unit (PRU) with the VerifyNow®, High on-treatment Platelet Reactivity (HTPR), and percentage of platelet inhibition will be assessed at Day 1 (pre-dosing) and treatment week 4 (visit 3). The PRU will be assessed immediately before dosing as that will assess the steady state which is the most appropriate approach for a maintenance dose. For clopidogrel assessment, Day 1 (before prasugrel switch dosing) is selected as being the last day of clopidogrel 75 MD after maximum 4 weeks screening (suggested test timing for clopidogrel 75 mg  $\geq$  6 days of maintenance). For prasugrel assessment, Week 4 is selected as being the last day of prasugrel 3.75 mg MD after 4 weeks treatment Period 1 (suggested test timing for prasugrel 5 mg  $\geq$  5 days on maintenance).

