## 11.0 Statistical Methods and Determination of Sample Size

### 11.1. Statistical and analytical plans

The statistical analysis will be performed by the Department of Biostatistics of Linical, using SAS® version 9.4 or later.

Statistical significance will be assessed for two-sided probability values  $< 0.05$ .

All descriptive variables will be tabulated. Quantitative variables will be described showing their number of available and missing observations, mean, median, standard deviation (SD), the range (minimum and maximum) and the first and third quartiles. Frequency and percentage will describe qualitative variables. Missing values will be tabulated with their frequency but will not be included in the calculation of percentages.

The main population for both the efficacy (antiplatelet effect) and the safety analysis will be the safety population (SAF), defined as all the subjects who have received at least one dose of study treatment. A Per Protocol (PP) population, defined as all the subjects of the safety population who do not perform any major protocol deviation

Full details of the statistical analysis will be given in a Statistical Analysis Plan (SAP) which will be prepared, approved and signed before the database closure, and so before the subjects' evaluability assessment.

Any deviation from the original SAP will be included and reported in the clinical study report (CSR).

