### 11.1.3 Efficacy Analyses

#### 11.1.3.1 Primary Efficacy Analyses

##### 11.1.3.1.1 PERIOD 1 (4 weeks)

Mean change in the P2Y12 reaction unit (PRU) value assessed with VerifyNow® from baseline to the end of the 4-week MD treatment period, after switching from clopidogrel MD to prasugrel MD will be analyzed with a paired t-test model. Mean changes will be presented with their corresponding 95% confidence interval.

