## 11.1.6 Other Analyses

No other analyses are planned.

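### The two secondary antiplatelet endpoints, HTPR and percent inhibition, have no planned within-patient change with a confidence interval, although both are measured before and after the switch

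*Combined protocol and SAP*

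**What the plan says.** Section 6.1.1.2 sets the Period 1 secondary objective: "To assess the antiplatelet effect and safety of prasugrel from baseline to the end of the 4-week MD treatment period". It names HTPR and percent platelet inhibition as the antiplatelet measures.

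Section 8.4.1.9 says that PRU, HTPR and percent inhibition "will be assessed at Day 1 (pre-dosing) and treatment week 4 (visit 3"). The schedule in Appendix 18.1 agrees. Day 1 is the last clopidogrel value and Week 4 the prasugrel value, in the same subjects. Section 8.4.1.7 notes that PRU is used "also to derive the platelet reactivity [HTPR"].

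Section 11.1.3.2.1 plans two secondary efficacy analyses:

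- Inhibition: "Percentage of platelet inhibition at the end of the 4-week MD treatment period, after switching from clopidogrel MD to prasugrel MD will be obtained", with a 95% confidence interval.
- HTPR: "Percentage of High on-Treatment Platelet Reactivity (HTPR) defined as PRU > 235 will be summarized with their corresponding 95% confidence interval". No visit is named.

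The endpoint and analysis text in the Summary (2.0) and Sections 6.2.1.2 and 8.4.3.1.2 matches this and defines no change for either measure. For PRU, by contrast, Section 11.1.3.1.1 specifies a mean change from baseline that "will be analyzed with a paired t-test model" and is reported with a 95% interval. Section 11.1.6 adds: "No other analyses are planned".

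**The concern.** The study has one arm, so each subject's Day 1 value on clopidogrel is the only comparator. A mean percent inhibition at Week 4 describes a level on prasugrel. It does not say how far the switch moved it.

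For HTPR the plan may intend one percentage or one per visit. Two visit-wise percentages with separate intervals would still give no interval for the change, and they ignore the pairing. They could also rest on different subjects, because Section 11.1 says: "Missing values will be tabulated with their frequency but will not be included in the calculation of percentages". A fall in HTPR between visits could then partly reflect who lacks a Week 4 test.

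At stake is the secondary objective only. Under the plan as written, the trial would report no interval for the change in the share of patients above PRU 235, or for the change in percent inhibition.

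**Working it through.** **1. Text comparison (no assumptions needed)**

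| Measure | Objective | Measured | Planned analysis |
|---|---|---|---|
| PRU | baseline to Week 4 (6.1.1.1) | Day 1, Week 4 | paired mean change with CI (11.1.3.1.1) |
| Percent inhibition | baseline to Week 4 (6.1.1.2) | Day 1, Week 4 | Week 4 level with CI (11.1.3.2.1) |
| HTPR | baseline to Week 4 (6.1.1.2) | Day 1, Week 4 | percentage with CI, visit not given (11.1.3.2.1) |

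The objectives for PRU and for the two secondary measures use the same time phrase. Only for PRU is it carried through to a change.

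**2. Sample size**

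The plan states no precision or power for HTPR or percent inhibition, so there is no figure to reproduce for them. The number used below comes from Section 11.2: 170 completers, from 170 / (1 − 0.15) = 200 enrolled, which reproduces.

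**3. Illustrative precision with n = 170 pairs**

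The documents give no HTPR rate, no SD for percent inhibition and no within-patient correlation. Every input in this step is an assumption.

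*Percent inhibition.* Level half-width = t(169) × SD / √170, with t = 1.974:
- SD 15, 20, 25 gives ±2.3, ±3.0, ±3.8 points.

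Paired-change half-width = t × SD × √(2(1 − ρ)) / √170, with SD 20 at each visit:
- ρ = 0.3: ±3.6
- ρ = 0.5: ±3.0
- pairing ignored (ρ = 0): ±4.3

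Pairing narrows the interval by 1 − √(1 − ρ), that is 16% and 29%. At ρ = 0.5 the change has the same half-width as the Week 4 level, but it answers a different question.

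*HTPR.* With p1 on Day 1, p2 at Week 4 and phi correlation φ:
- p11 = p1p2 + φ√(p1(1 − p1)p2(1 − p2)); b = p1 − p11; c = p2 − p11
- paired half-width = 1.96 × √((b + c − (b − c)²) / 170)
- unpaired half-width = 1.96 × √((p1(1 − p1) + p2(1 − p2)) / 170)

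| Assumed rates | φ | b, c | Paired | Unpaired | Narrower by |
|---|---|---|---|---|---|
| 25% to 15% | 0.1 | 0.197, 0.097 | ±8.0 | ±8.4 | 5% |
| 25% to 15% | 0.3 | 0.166, 0.066 | ±7.1 | ±8.4 | 16% |
| 25% to 15% | 0.53 | 0.131, 0.031 | ±5.8 | ±8.4 | 31% |
| 30% to 10% | 0.3 | 0.229, 0.029 | ±7.0 | ±8.2 | 15% |

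**4. Different denominators**

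Suppose 200 subjects have a Day 1 value, some lack a Week 4 value, and Day 1 HTPR is 40% in those and 25% in the rest (assumed).
- 10 missing: (190 × 0.25 + 10 × 0.40) / 200 = 25.75%, against 25% in subjects with both values, a difference of 0.75 points.
- 30 missing: (170 × 0.25 + 30 × 0.40) / 200 = 27.25%, a difference of 2.25 points.

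That much apparent fall would come from missing subjects alone. The 30-subject case spends the whole 15% dropout allowance, which covers all 28 weeks, within the first four. It is an upper case.

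**The case against.** **The objective may only describe an observation window.** The same phrase in Section 6.1.1.2 covers safety, where it can only mean a period. Inhibition is consistently defined and analysed as a Week 4 level, so endpoint and analysis agree with each other. That agreement is real. But Section 6.1.1.1 uses the same phrase for PRU, and there the plan implements it as a paired change. A level without a comparator also does not show an effect of switching, whichever way the phrase is read.

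**HTPR is scheduled at only two visits, and the wording may mean both.** This is plausible, and naming the visits is then a clarification. Two separate intervals are still not an interval for the change.

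**PRU already gives a paired estimate of the switch effect, and HTPR is a cut of PRU.** This stands and limits the consequence. A mean PRU change does not, however, say how many patients crossed 235.

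**A separate SAP is promised in Section 11.1.** It could add these analyses, and it is not among the documents supplied, so the gap is in the plan as supplied. Missing data (11.5) and subgroups (11.7) are specifically deferred to it; the secondary efficacy estimates are not. The SAP need only be signed before database closure, whereas Section 11.4 has Period 1 analysed once the last patient completes four weeks.

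**The figures are assumed, and the unpaired comparison is not one the plan proposes.** Correct. They show what a paired analysis would deliver and do not measure a loss in the plan. Missing counts will be tabulated (11.1), so unequal denominators would be visible, and Section 8.5.2 requires platelet tests at early termination before Visit 3, which limits missing values.

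**Conclusion.** The concern holds. As written, the plan contains no estimate of change with a confidence interval for either secondary antiplatelet endpoint, although the objective runs from baseline and both measures are taken before and after the switch in the same subjects. That conclusion rests on the text alone.

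The size is modest: the primary PRU result, the sample size and the safety analyses are unaffected. The precision and dropout figures depend entirely on assumed rates, SDs and correlations. They support only two statements: a paired estimate is feasible at 170 completers, and unequal denominators could shift an apparent HTPR change by about one to two points under the stated assumptions. The change should be made because it is cheap and makes the secondary objective answerable.

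**What to change.** In Section 11.1.3.2.1, with matching wording in the Summary (2.0) and Sections 6.2.1.2 and 8.4.3.1.2:

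1. **HTPR.** Report Day 1 and Week 4 in subjects with both values, with a 2×2 shift table and the paired difference in proportions with a matched-data 95% confidence interval. McNemar's test is optional.
2. **Percent inhibition.** Report the mean within-patient change with a 95% interval from the paired t distribution, as for PRU.
3. **Clarifications.** Name the visit or visits for the planned HTPR percentage and the number of subjects behind each. State whether a platelet test at an early-termination visit before Visit 3 counts as the Week 4 value; this bears on PRU as well.

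Keep the planned percentages. The SAP can carry the detail, provided it is settled before the Period 1 analysis.

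The cost is a few table rows from data already collected, small wording changes in the endpoint and summary text, and two more secondary estimates with no multiplicity adjustment, in line with Section 11.6. No extra patients, visits or tests are needed.

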##### 11.1.3.2.2 PERIOD 2 (+24 weeks [optionally up to a maximum 12 months of P2Y12 inhibitor treatment after ACS underwent PCI, based on investigator's discretion])

Period 2 will include just safety analyses.

### 11.1.4 Safety Analyses

#### 11.1.4.1 Primary Safety Analysis

##### 11.1.4.1.1 PERIOD 1 (4 weeks)

Period 1 will include just efficacy analyses (antiplatelet effect) as primary endpoint.

##### 11.1.4.1.2 PERIOD 2 (+24 weeks [optionally up to a maximum 12 months of P2Y12 inhibitor treatment after ACS underwent PCI, based on investigator's discretion])

Incidence of major bleeding events (non-coronary artery bypass grafting [CABG] thrombolysis in myocardial infarction (TIMI) major) after 28 MD treatment weeks (optional maximum 12-month P2Y12 inhibitor treatment after ACS underwent PCI) will be summarized with their corresponding 95% confidence interval, including median times to events as per Kaplan-Meier estimates.

## 11.1.4.2 Secondary Safety Analysis

### 11.1.4.2.1 PERIOD 1 (4 weeks)

Incidence of events after 4 MD treatment weeks (major bleeding events, minor or clinically relevant bleeding events, major adverse cardiovascular events) will be summarized with their corresponding 95% confidence interval, including median times to events as per Kaplan-Meier estimates.

Percentage of all cause deaths and adverse events after 4 MD treatment weeks will be summarized with their corresponding 95% confidence interval.

### 11.1.4.2.2 PERIOD 2 (+24 weeks [optionally up to a maximum 12 months of P2Y12 inhibitor treatment after ACS underwent PCI, based on investigator's discretion])

Incidence of events after 28 MD treatment (optional maximum 12-month P2Y12 inhibitor treatment period after ACS underwent PCI) (minor or clinically relevant bleeding events, major adverse cardiovascular events, stent thrombosis and revascularization) will be summarized with their corresponding 95% confidence interval, including median times to events as per Kaplan-Meier estimates.

Percentage of all cause deaths and adverse events after 28 MD treatment (optional maximum 12-month P2Y12 inhibitor treatment period after ACS underwent PCI) will be summarized with their corresponding 95% confidence interval.

## 11.1.5 Exploratory Analyses

Association of primary and secondary variables with CYP2C19 genotype will be evaluated. Similar analysis to the described above may be obtained per genotype subgroups when appropriate for the size of the subgroup.

## 11.1.6 Other Analyses

No other analyses are planned.

## 11.2. Determination of sample size

A total of 200 patients will be enrolled to have 170 completed patients in the study (expected drop-out rate of 15%).

The proposed total sample size of 170 completed patients will allow to estimate a mean PRU value with a precision of around 10% and a confidence level of 95%, considering a standard deviation of 70 (Han-Young Jin, 2014).

The probability that 1 or more adverse reactions (or other events) will occur in a sample of 170 patients with an anticipated incidence rate of 0.01 is 0.82%. So this sample achieves a power of 82% to find adverse events with incidences close to 0.01.

This sample size will also permit enough power to detect a statistically significant reduction of the P2Y12 ( $\neq 0$ ), considering an effect size around 0.40 ( $\mu=30$ ,  $SD=70$ ), using a significance level of 0.05 and a two-sided one-sample t-test.

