disposable cartridges that can be used to monitor different antiplatelet drugs: aspirin, clopidogrel and glycoprotein (GP) IIb/IIIa therapy. The PRU will be assessed immediately before dosing as that will assess the steady state which is the most appropriate approach for a maintenance dose. For clopidogrel assessment, Day 1 (before prasugrel switch dosing) is selected as being the last day of clopidogrel 75 MD after 4 weeks screening (suggested test timing for clopidogrel 75 mg  $\geq$  6 days of maintenance). For prasugrel assessment, Week 4 is selected as being the last day of prasugrel 3.75 mg MD after 4 weeks treatment Period 1 (suggested test timing for prasugrel 5 mg  $\geq$  5 days on maintenance).

The study has been designed with 2 periods: the first one to assess the platelet function after 4 weeks, and a longer period up to 28 weeks for a mid-term safety assessment of bleeding events, major adverse cardiovascular events (MACE), and all cause deaths. Based on the investigator's discretion, patients will be offered to extend Period 2 up to maximum 12 months of P2Y12 inhibitor treatment after ACS underwent PCI for an additional safety assessment of the same objectives.

The study sample size is based on the expected PRU change from baseline after 4 weeks of treatment based on a previously published reference. We consider the antiplatelet effect of prasugrel in PRU value assessed with VerifyNow® can be observed within 4 weeks which is a valid recall period, assessing other safety endpoints during a longer Period 2 (+24 weeks; or optionally up to a maximum 12 months of P2Y12 inhibitor treatment after ACS underwent PCI based on investigator's discretion). The selected sample size will be also enough for an 82% probability that 1 or more adverse reactions (or other events) will occur with an anticipated incidence close to 0.01.

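### Does the 0.82% printed for the chance of seeing at least one event, or the unanchored 10% precision, undermine the sample-size justification?

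*Combined protocol and SAP*

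**What the plan says.** Section 11.2 of the protocol, repeated almost word for word in the Summary, enrols 200 patients to obtain 170 completers, allowing 15% drop-out. It then offers three supports for 170.

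- **Precision.** The sample will "estimate a mean PRU value with a precision of around 10% and a confidence level of 95%, considering a standard deviation of 70", with the SD credited to a published comparison. No mean PRU is given.
- **Rare events.** The probability of one or more events among 170 patients "with an anticipated incidence rate of 0.01 is 0.82", printed with a percent sign. The following sentence reads "So this sample achieves a power of 82% to find adverse events with incidences close to 0.01".
- **Power for the change in PRU.** A two-sided one-sample t-test at the 0.05 level, "considering an effect size around 0.40", with mean 30 and SD 70.

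Section 7.2 covers the same ground. It says "The study sample size is based on the expected PRU change from baseline after 4 weeks of treatment", and it gives the rare-event figure as "an 82% probability that 1 or more adverse reactions (or other events) will occur with an anticipated incidence close to 0.01".

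**The concern.** Two things catch the eye.

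The first is a plain contradiction. A probability of 0.82% says the study has less than one chance in a hundred of seeing an event that affects one patient in a hundred. The next sentence says 82%. The slip appears in two separate sections, so it is unlikely to come from reading the PDF. It also bears on safety, and the Period 2 primary endpoint is major bleeding. If the lower figure were right, the sample would be far too small to support the safety aim.

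The second is that a percentage precision for a mean cannot be checked without the mean, and the text does not say whether it refers to the half-width or the full width of the interval. The value 70 is also used twice, once for a mean PRU and once for the change in PRU. These quantities share an SD only if the within-patient correlation is 0.5. If 70 describes single values and the correlation is lower, the change varies more than the power statement assumes.

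**Working it through.** **Inputs, all from Section 11.2:** 200 enrolled, 170 completers, 15% drop-out, incidence 0.01, SD 70, mean change 30, two-sided 0.05. The documents give no mean PRU and no within-patient correlation, so values for those below are assumptions.

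**Drop-out.** 170 / 0.85 = 200. The plan's figure reproduces.

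**Chance of at least one event.** P = 1 − (1 − p)^n = 1 − 0.99^170 = 1 − 0.181 = 0.819. This matches the stated 82%. Other readings do not produce 0.82%:

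| Reading | Probability |
|---|---|
| Exact, n = 170, p = 0.01 | 81.9% |
| Poisson, 1 − exp(−1.7) | 81.7% |
| n = 200, p = 0.01 | 86.6% |
| n = 170, incidence read as 0.01% | 1.7% |

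Only the proportion 0.82, with the percent sign removed, fits.

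**Precision of a mean.** The standard error is 70 / √170 = 5.37 PRU.

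- Half-width: 1.96 × 5.37 = 10.5 PRU (10.6 with the t quantile).
- Full width: about 21 PRU.
- Mean at which the half-width is exactly 10%: 10.5 / 0.10 = 105 PRU (106 with t).
- Mean at which the full width is exactly 10%: about 210 PRU (212 with t).

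At assumed means of 100, 150, 200 and 250 PRU, the t half-width is 10.6%, 7.1%, 5.3% and 4.2% of the mean. Read as a half-width, around 10% is met or bettered over this range, allowing for rounding at 100.

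**Power for the change, as written.** The effect size is 30 / 70 = 0.43, which the plan rounds down to about 0.40. With 170 pairs the one-sample t-test has power 99.98% at 0.43 and 99.94% at 0.40.

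**Power if 70 is the SD of single values.** The SD of the change is then 70 × √(2(1 − r)), where r is the assumed correlation between the two measurements.

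| r | SD of change | 95% half-width (t) | Power for 30 PRU |
|---|---|---|---|
| 0 | 99.0 | 15.0 | 97.6% |
| 0.25 | 85.7 | 13.0 | 99.5% |
| 0.5 | 70.0 | 10.6 | 99.98% |
| 0.75 | 49.5 | 7.5 | above 99.99% |

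The SD of the change falls as r rises, so r = 0 is the worst case among non-negative correlations.

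**The case for a change.** The strongest case for acting is that a sample-size justification tends to be carried into the SAP and the study report. A figure wrong by a factor of 100 should not travel with it, least of all beside a sentence that contradicts it. A reader should not have to work out which of two adjacent numbers is meant. The same argument asks for the precision in PRU units, or with its base, and for a label on the SD, because a half-width of 10.5 PRU can be quoted for the mean change only if 70 is the SD of that change.

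What stands is that the printed 0.82% is wrong, and that the precision sentence leaves out details a careful author would include. What does not stand is any consequence for the trial. The correct 82% follows immediately in both places and appears again in Section 7.2, so nothing rests on the wrong number. Section 7.2 ties the sample size to the PRU change, not to the 10% statement. The power sentence pairs a mean of 30 and an SD of 70 with a one-sample t-test, and its natural reading is that 70 is the SD of the change. The base for the 10% may lie in the cited comparison; the documents do not settle this. The interval in the analysis will be computed from the observed data whatever the planning sentence said.

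**Conclusion.** The misprint is real but clerical: 81.9% is shown as 0.82% in two places, and the correct value stands beside it each time. The 10% precision is under-described, not erroneous: about 10.5 PRU as a half-width, which is 10% or better once the mean reaches about 105 PRU. The unlabelled SD could lower power for a 30-PRU change from 99.98% to 97.6% at worst, assuming 170 complete pairs and a correlation that is not negative. Under any of these readings the 170 completers and 200 enrolled remain adequate for the stated purpose, and no endpoint, analysis or conclusion shifts. The figure could be tidied whenever the text is next reissued, but the plan needs no change on this account.

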### **EXPLORATORY VARIABLES**

Association of primary and secondary variables with CYP2C19 genotype will be evaluated. Similar analysis to the described above may be obtained per genotype subgroups when appropriate for the size of the subgroup.

**Sample size Justification:** A total of 200 subjects will be enrolled to have 170 completed subjects in the study (expected drop-out rate of 15%).

The proposed total sample size of 170 completed subjects will allow to estimate a mean PRU value with a precision of around 10% and a confidence level of 95%, considering a standard deviation of 70 (Han-Young Jin, 2014).

The probability that 1 or more adverse reactions (or other events) will occur in a sample of 170 subjects with an anticipated incidence rate of 0.01 is 0.82%. So this sample achieves a power of 82% to find adverse events with incidences close to 0.01.
 
This sample size will also permit enough power to detect a statistically significant reduction of the P2Y12 (<math>\neq 0</math>), considering an effect size around 0.40 (<math>\mu=30</math>, <math>SD=70</math>) (Han-Young Jin, 2014), using a significance level of 0.05 and a two-sided one-sample t-test.
	

Interim analysis: No interim analysis is planned; however, the Period 1 analyses (both primary and secondary) will be analyzed separately per protocol.
	

Study schedule and anticipated date of completion
	
May-Jul 2018: EC/IRB/Health Authorities submission          Nov 2018 - Aug 2020: Recruitment and treatment period          Sep-Oct 2020: Database lock          Jan-Feb 2021: Clinical Study Report

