#### **6.1.2 PERIOD 2 (+24 weeks [optionally up to a maximum 12 months of P2Y12 inhibitor treatment after ACS underwent PCI, based on investigator's discretion])**

##### **6.1.2.1 Primary Objective**

To assess the safety of prasugrel on major bleeding events from baseline to the end of the 28-week MD treatment period (optional maximum 12-month P2Y12 inhibitor treatment period after ACS underwent PCI), after switching from clopidogrel MD to prasugrel MD.

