### 6.2.2 PERIOD 2 (+ 24 weeks [optionally up to a maximum 12 months of P2Y12 inhibitor treatment after ACS underwent PCI, based on investigator's discretion])

#### 6.2.2.1 Primary Endpoint

The primary endpoint will be the incidence of major bleeding events (non-coronary artery bypass grafting [CABG] thrombolysis in myocardial infarction (TIMI) major) after 28 MD treatment weeks or up to maximum 12-month P2Y12 inhibitor treatment after ACS underwent PCI.

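### Does the 82% "power" sentence leave the Period 2 major-bleeding endpoint without a usable sizing statement?

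*Combined protocol and SAP*

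**What the plan says.** Period 2 has its own primary objective in Section 6.1.2.1, "To assess the safety of prasugrel on major bleeding events from baseline to the end of the 28-week MD treatment period", with an optional extension to 12 months of P2Y12 inhibitor treatment. Section 6.2.2.1 makes it an endpoint: "The primary endpoint will be the incidence of major bleeding events", using the non-CABG TIMI major definition. Under Section 11.1.4.1.2 the incidence "will be summarized with their corresponding 95% confidence interval, including median times to events as per Kaplan-Meier estimates". Section 11.1.4.2.1 treats the 4-week data in the same way: "Incidence of events after 4 MD treatment weeks (major bleeding events, minor or clinically relevant bleeding events, major adverse cardiovascular events".

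Section 11.2 makes four sizing statements: 200 enrolled to give 170 completers, the precision of a mean PRU, a safety sentence, and a t-test on PRU change. The safety sentence, repeated in the Summary, opens "The probability that 1 or more adverse reactions (or other events) will occur in a sample of 170 subjects". It continues "with an anticipated incidence rate of 0.01 is 0.82", followed by a percent sign, and ends "So this sample achieves a power of 82% to find adverse events with incidences close to 0.01". Section 7.2 gives the same number differently: "The selected sample size will be also enough for an 82% probability". That section also says the sample size rests on the 4-week PRU change.

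Sections 11.1 and 11.1.1 make the safety population (every dosed subject) the main analysis set. Section 11.1 leaves full statistical details to a SAP signed before database closure.

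**The concern.** Major bleeding is one of the trial's two primary endpoints, yet the only sizing that touches it is a detection probability labelled as power. That probability does not say how precisely the incidence will be estimated. The 1% is attached to no period, although bleeding is analysed at 4 weeks, at 28 weeks and optionally later. It is also a generic event rate, not an anticipated major-bleeding rate. The interval method is unnamed, and at the counts a 1% rate implies (170 × 0.01 = 1.7 events) a poor choice would matter: a normal-approximation interval on zero events has zero width. The calculation uses 170 completers, while the analysis uses all dosed subjects.

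If these points had consequences, a result of no or few bleeds could be presented as evidence of safety from a design with 82% power, when the data would be compatible with several times the 1% rate.

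**Working it through.** **Inputs.** From Section 11.2: n = 170 completers, 200 enrolled, 15% drop-out (200 × 0.85 = 170), incidence 0.01. From Section 11.1: the main analysis set is all dosed subjects, so up to 200. Assumptions: 1% is borrowed for illustration, because the documents give no major-bleeding rate; the denominator of 200 requires every enrolled subject to be dosed.

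**1. The plan's own figure.** P(at least one event) = 1 − (1 − p)^n = 1 − 0.99^170 = 1 − 0.1811 = 0.8189, or 82%. The version printed with a percent sign is too small by a factor of 100, and the next sentence gives the right value. With 200 dosed, 1 − 0.99^200 = 0.866, so using completers understates the probability for the planned analysis set.

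**2. Precision the endpoint will have.** Two-sided exact (Clopper-Pearson) 95% limits; for zero events the upper limit is 1 − 0.025^(1/n).

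| Events | n = 170 | n = 200 |
|---|---|---|
| 0 | 0 to 2.15% | 0 to 1.83% |
| 1 | 0.01 to 3.23% | 0.01 to 2.75% |
| 2 | 0.14 to 4.19% | 0.12 to 3.57% |
| 3 | 0.37 to 5.07% | 0.31 to 4.32% |

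**3. Does zero events fail to exclude 2%?** At n = 170 the exact limit is 2.15% and the Wilson limit 2.21%, so 2% is not excluded. At n = 200 they are 1.83% and 1.89%, so it is. For the exact method the change comes at n = 183. Even at n = 170, a Jeffreys interval (1.46%) or a one-sided 95% exact bound (1.75%) excludes 2%. Nor is it true that no result excludes 2%: 8 events in 170 give 2.05 to 9.06%, which excludes it from below.

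**4. Interval method.** Exact and Wilson limits nearly coincide: at n = 170 the upper limits are 2.15% and 2.21% for zero events, and 4.19% by both for two. Jeffreys and Agresti-Coull spread wider at zero events (1.46% and 2.66%). The normal approximation breaks down visibly: 0 to 0% for no events, −0.56 to 1.74% for one. Nothing in the plan prescribes it.

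**5. Risk period.** Assume a constant hazard and 170 subjects fully followed. If 1% is the 28-week risk, the 4-week risk is 1 − 0.99^(4/28) = 0.143% and P(at least one) by week 4 is 22%. If 1% is a 52-week risk, the 28-week risk is 1 − 0.99^(28/52) = 0.540% and P is 60% by week 28 and 12% by week 4. The 82% therefore needs a period to be read exactly, but no planned analysis uses it as an input.

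**The case for a change.** The strongest case for a change is that precision is the natural sizing measure for a descriptive endpoint, and the plan supplies it for PRU but not for its other primary endpoint. The risk of misreading is also real. At n = 170, three or fewer events occur with probability 91% if the true rate is 1%, but still 56% at 2% and 25% at 3%, so a low count discriminates poorly. Calling the sizing figure power invites over-reading, and nothing commits the SAP to correct the label or attach a period.

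What stands is the description: the term is loose, the period is absent, and the interval method and expected width are not stated in the protocol. What does not stand is the consequence. The sentence before the label defines the quantity as the chance of one or more events. Period 2 has no hypothesis, comparator or success limit for an inflated power claim to support. The reported 95% interval will itself show the reader what a low count leaves open. The interval method is the kind of detail Section 11.1 assigns to the SAP. It is also better settled there: the same analysis uses Kaplan-Meier, and with 15% drop-out expected, a simple binomial interval on all dosed subjects would count early leavers as event-free to week 28.

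**Conclusion.** No change to the plan is needed. The 82% is correct as a detection probability (0.819 at 170 subjects, 0.866 at 200). The stray percent sign is a clerical slip corrected by the sentence after it, and the word power is loose usage that Section 7.2 avoids. The missing period, interval method and precision statement are gaps in a descriptive analysis that an analyst would fill in the SAP with a method suited to small counts. Filling them would alter neither enrolment, visits and data nor what the trial can conclude.

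The limited precision is real and worth remembering when the result is read: one event gives an exact upper limit of 3.23% at 170 or 2.75% at 200. The claim that zero events cannot exclude 2% depends on the denominator and the method, and it fails at the planned safety set if at least 183 subjects are dosed and a two-sided exact interval is used. All event-count expectations here rest on the generic 1%, which the documents do not offer as a major-bleeding rate.
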